## CHAPTER 9 STUDY COMPLETION AND CLOSEOUT PROCEDURES

### 9.1 Study End

After the study intervention and data collection periods are completed, the study team will share results with all site PIs and engage them throughout the analysis and manuscript writing process and provide sites who participated in the control arm with a training and materials package aimed to facilitate implementation should they desire.

### 9.2 Dissemination Policy

Access to a cleaned, deidentified dataset and code may be requested after the study is completed and accompanying manuscripts are published. As required by NIH, data will be submitted to FITBIR. The primary aim is a study-wide analysis and will be disseminated as such. We do not expect to have sufficient data for publication at the level of individual sites. Any publications and presentations prior to the release of the primary results will not impede the integrity of those results.

**APPENDIX 2: ABBREVIATIONS**

AIS-Abbreviated Injury Score

BTF-Brain Trauma Foundation

CIIC-Centro de Informática e Investigación Clínica

CNH-Children's National Hospital

Protocol-PEGASUS Argentina

DIBQ-Determinants of Implementation Behavior Questionnaire

DSMB-Data and Safety Monitoring Board

FITBIR-Federal Interagency Traumatic Brain Injury Research

GCS-Glasgow Coma Scale

GOS-Glasgow Outcome Scale

GOSE-Peds-Glasgow Outcome Scale Extended Pediatric

ICU-Pediatric Intensive Care Unit

IRB-Institutional Review Board

ISS-Injury Severity Score

ITT-Intent-To-Treat

MI-Motivational Interview

MPI-Multiple Principal Investigator

NIH-National Institutes of Health

NINDS-National Institute of Neurological Disorders and Stroke

PAHO-Pan-American Health Organization

PEGASUS-Pediatric Guideline Adherence and Outcomes

PI-Principal Investigator

RCT-Randomized Controlled Trial

TBI-Traumatic Brain Injury

TDF-Theoretical Domain Framework

UW-University of Washington

VSM-Value Stream Map

WHO-World Health Organization

WSU-Washington State University

## Analysis plan Aim 1A \_ PEGASUS Argentina \_ 031022

**Paper title:** TBD

**Specific Aim 1:** Determine the relationship between PEGASUS program implementation and TBI guideline adherence (Aim 1a)

*Hypothesis: Centers that receive the PEGASUS program have higher TBI guideline adherence (main outcome), as well as better discharge survival and 3-month Glasgow Outcome Scale-Extended (GOSE) score (secondary outcomes) than centers who receive usual care.*

**Authors:** TBD

**Questions of interest:**

- 1) Does PEGASUS implementation improve guideline adherence?
- 2) Are there any imbalances between the study arms that need to be addressed?

**Study Design:** 2-arm parallel cluster RCT

**Study population:** Pediatric (<18) ICU patients with severe TBI at 16 sites

**Exposure variable(s):** Study Arm (binary)

**Outcome variable(s):** (1) TBI guideline adherence

*"The main outcome is TBI guideline adherence during first 3 days ICU stay, calculated via our previously developed TBI guideline adherence scorecard. Using patient charts, we measure presence or absence of adherence to the indicators and capture time since injury for any observed indicators, including the main protective KPIs (ventilation, nutrition, CPP). Patient guideline adherence is defined as the sum of indicators to which care was adhered divided by the number of relevant adherence indicators for a given patient. Mean adherence scores are calculated for each site individually and across all sites."*

Describe:

- (2) Extracranial injuries
- (3) Discharge GOS
- (4) Discharge survival
- (5) 3-month GOSE-Peds
- (6) 3-month mortality
- (7) KPIs?

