### 3.3 Site Randomization Plan

Sixteen study sites were recruited by CIIC based on willingness to participate and annual severe TBI admissions. Sites were added after the original proposal to increase the potential patient recruitment population. All sites receive compensation for data submission. Prior to randomization on July 13, 2020, three sites who had no or one enrolled patient during ten months of baseline usual care data collection were removed from the pool. The remaining sixteen sites participating were ranked by median monthly baseline enrollment, number of zero recruiting months, and total number of recruited patients and divided into four groups (Group A=highest enrollment group, Group D=lowest enrollment group). The study statistician performed computer block randomization within each group to assign to control and intervention arms at a 1:1 ratio. Participant assignment was dependent on the intervention or control arm assignment of the study hospital to which they were admitted.

Due to the nature of the intervention study team, site staff, and patients' families are aware of the site's arm assignment.

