### **3.7 Sample Size and Power**

A sample size of 432 participants is targeted for the planned parallel cluster study, which would have 80% power to detect a 18.7% higher ICU TBI guideline adherence rate with program implementation at the site level, with a two-sided alpha of 5%, and an intraclass coefficient of 0.05. Calculations included 58.6% guideline adherence rate estimate based on prior pilot work in Argentina and assumed no change in adherence rate at control sites. The study will not be sufficiently powered for secondary outcomes of patient mortality, discharge outcomes, or three-month follow-up outcomes.

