#### 8.4 Data Collection Timeline

Baseline data collection will occur at all participating sites from September 2019-September 2020. From October 2020-September 2023, intervention sites will collect additional data associated with the intervention implementation. The Data Collection Timeline below shows the data types collected (leftmost column) and the intervals of repeated measures.

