**Methods:**

1. Descriptive statistics for all measures at the facility level, within treatment and control arms. Potential differences in patient (age, sex, race/ethnicity) and injury characteristics will be examined using bivariate analyses by center using  $\chi^2$  tests (categorical) and t-tests (continuous).
2. ITT analysis: multi-level mixed effects Poisson regression with robust variance estimation and clustering by site to estimate the relative risk of PEGASUS implementation on TBI guideline adherence and stratified by extracranial injury, as described in Zou, et al.  
Per protocol: As with ITT, but potentially including implementation dose/fidelity as covariate and interaction with intervention.
3. Secondary analyses (Following ITT for primary analysis): Poisson regression with robust variance estimation and clustering by site to estimate separately the relative likelihood of program implementation on these outcomes: 1) in-hospital mortality; and 2) GOSE-Peds at 3 months post TBI, analyzing GOS score as a dichotomous measure (minor-moderate impairment vs major impairment-vegetative state and death).  
Multivariable Cox regression model to examine the marginal effect of PEGASUS on mortality during the 3 months post discharge, averaged over all centers.
4. Sensitivity analyses: repeated analysis on ICP monitoring patients
5. Subgroups: COVID effect and geographic effect

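### The Aim 1a analysis sets no admission window and leaves out site baseline adherence, so it gives up precision and protection against chance imbalance between 8 and 8 sites

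*SAP*

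**What the plan says.** Protocol 8.4 states: "Baseline data collection will occur at all participating sites from September 2019-September 2020". The programme then runs from October 2020 to September 2023 (Protocol Chapter 4 and 8.4).

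Protocol 3.3 shows that site selection and stratification used early baseline enrolment. It excludes some sites beforehand: "Prior to randomization on July 13, 2020, three sites who had no or one enrolled patient during ten months of baseline usual care data collection". The remaining 16 were ranked on enrolment measures and randomised within four groups. Prior adherence played no part.

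The SAP defines its population as severe-TBI ICU patients under 18 at the 16 sites, without dates. Its exposure entry reads "Exposure variable(s): Study Arm (binary". Its covariates cover patient, implementation and organisational factors (trauma volume and staffing), but neither period nor baseline adherence. The primary analysis is a "multi-level mixed effects Poisson regression with robust variance estimation and clustering by site to estimate the relative risk of PEGASUS implementation on TBI guideline adherence".

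The sample-size section (Protocol 3.7) "assumed no change in adherence rate at control sites".

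**The concern.** Two things are missing from the SAP.

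First, the analysis set is not stated. Children from about a year of usual care are in the same database, at the same sites, and carry the same arm label. Nothing in the SAP text keeps them out of the primary comparison.

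Second, prior site adherence is the obvious prognostic variable for site adherence, and the plan does not use it. With 8 sites per arm and stratification on enrolment only, the arms can differ by chance in how well they followed the guidelines before the programme. That chance difference forms part of the error of the primary estimate, and baseline data could remove some of it.

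**Working it through.** **1. Reproduce the plan's figure.** Protocol 3.7: "A sample size of 432 participants is targeted for the planned parallel cluster study", with "80% power to detect a 18.7% higher ICU TBI guideline adherence rate with program implementation at the site level". It takes alpha as 5% two-sided, the ICC as 0.05 and the control rate as 58.6%. Read as percentage points, the intervention rate is 58.6 + 18.7 = 77.3%.

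- Children per site: 432/16 = 27. Design effect: 1 + 26 x 0.05 = 2.30.
- Sites per arm (unpooled normal formula): (1.960 + 0.842)² x (0.586 x 0.414 + 0.773 x 0.227) x 2.30 / (27 x 0.187²) = 7.99, i.e. 8.
- Total: 8 x 27 x 2 = 432. The pooled formula gives 78.9% power.

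**2. Which children does 432 cover?** Protocol 3.8 gives about 9 per site per year, and the implementation period is 3 years: 16 x 9 x 3 = 432. The target is therefore filled by implementation-period children. Protocol 3.8 also uses baseline recruitment as the source of the forecast, not as part of the total.

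**3. Baseline children per site (assuming the same rate).** The full 13 months gives 9 x 13/12 = 9.75. September 2019 to 12 July 2020, about 10.4 months, gives 9 x 10.4/12 = 7.8. The working range is 8 to 10.

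**4. Variance that baseline could explain.** Reliability of a site mean from m children: L(m) = m x ICC / [1 + (m - 1) x ICC].

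- L(27) = 1.35/2.30 = 0.587
- L(7.8) = 0.39/1.34 = 0.291
- L(10) = 0.50/1.45 = 0.345

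Squared correlation of baseline and follow-up site means: r² = c² x L(baseline) x L(27), where c is the between-period correlation of true site effects. The documents do not give c; 0.6 to 1.0 is assumed.

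| Baseline per site | c | r² | Ideal variance change | Site-mean covariate |
|---|---|---|---|---|
| 7.8 | 0.6 | 0.061 | -6% | +2% |
| 7.8 | 1.0 | 0.171 | -17% | -10% |
| 10 | 0.6 | 0.073 | -7% | 0% |
| 10 | 1.0 | 0.202 | -20% | -14% |

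The ideal column is -r², the most a constrained-baseline model could achieve. The last column charges for estimating the slope from 16 sites: (1 - r²) x (1 + 1/12) - 1, where 1/12 is the mean of 1/χ² on 14 df. Simulated 16-site trials gave up to +3% at the unfavourable end, which I keep as the cautious limit. These are linear approximations on site means, not the Poisson model itself.

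**5. In power terms.** From 78.9%, the ideal limit is about 87% with 9.75 baseline children per site and c = 1. With c = 0 there is no gain.

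**6. Size of the chance imbalance.** The SD of the arm difference in true prior adherence is patient SD x √0.05 x √(2/8). A patient SD of 0.20 gives 2.2 points and 0.49 gives 5.5. Both SDs are assumed. The upper one is that of a yes/no outcome and is probably too large for a score defined as a fraction of indicators.

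**The case against.** The strongest reply is that nothing here biases the trial. The arms run concurrently, so secular or COVID-19 change common to both does not distort the comparison, and an implementation-period analysis needs no period term. Chance differences between sites are what the ICC and the clustering by site already allow for. SAP question 2 also undertakes to look for imbalances between arms. All of this stands, and it limits the point to precision and chance imbalance. SAP Methods item 1, however, names patient and injury characteristics for that check, not prior adherence.

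The gain may also be small. Only the ICC of 0.05 is documented. Protocol 3.3 shows unequal enrolment and removes only sites with no or one patient, so some baseline means will be noisy. With assumed baseline counts of 14, 9, 5.5 and 2.7 in the four enrolment groups, simulation put the site-mean change at about +2% to -5.5%. This also stands, and is a reason to prefer the constrained-baseline model.

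Three stronger readings are tempting but unsupported:

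- *Baseline children at intervention sites will be counted as exposed.* Pooling 16 x 9 x 13/12 = 156 baseline children with 432 would leave 156/588 = 27% of the intervention arm unexposed and shrink 18.7 points to 13.7, with power about 51% to 56%. The SAP wording does not exclude this, but no passage plans it and the 432 arithmetic points away from it.
- *The baseline data are discarded.* They are used to rank sites (Protocol 3.3) and as a safety reference (Protocol 5.1).
- *The baseline is wholly pre-randomisation.* It runs past 13 July 2020, so it is pre-implementation only.

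Several design and timeline figures are not shown in the text available, so what they say about the analysed period could not be checked.

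**Conclusion.** The point holds as a gap in specification and efficiency, not as a flaw in validity. The SAP should say which children are in the primary comparison and should use site baseline adherence, which it already has for every site.

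At ICC 0.05, with 8 to 10 baseline children per site and a between-period correlation of 0.6 to 1.0, the variance change is about +3% to -14% for a site-mean covariate and at best about -6% to -20% for a constrained-baseline model. A higher ICC would raise the gain: at an assumed 0.10, with 7.8 baseline children, r² is 0.125 to 0.348. The recruitment split and the correlation are assumptions.

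A reader might also infer that baseline data could rescue a contrast narrowed by improvement at control sites. They could not. No change at control sites is a power assumption, and a before-after change in one arm, spanning COVID-19, has no control of its own.

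**What to change.** 1. State in the SAP that the primary set is children admitted from October 2020 to September 2023, so that no baseline child is coded as exposed by arm.
2. Pre-specify adjustment for baseline adherence. Preferred: one model for both periods with a period effect, treatment defined as arm x follow-up period, the arms constrained equal at baseline, and random effects for site and site-by-period. Name the site-mean covariate as the fallback if that model does not converge.
3. Take the baseline from children admitted before 13 July 2020. Keep those admitted from then to 30 September 2020 outside both periods, because arms were known and pre-implementation training was due.
4. Score baseline children on the final scorecard, since Protocol 4.3 has sites giving input on its indicators during the baseline period.
5. Report the control arm's change from baseline as description only.

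The cost is SAP text, rescoring where indicators changed, and a slightly larger model to fit on 16 sites. The site-mean version may lose about 3% precision if the between-period correlation is low.

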**Covariates/confounders:**

- patient (demographics, ISS, LOS, presence of extracranial injuries, and surgery (yes/no) for up to 7 days after severe TBI in case report forms. If a child is discharged or dies prior to day 7, data collection will stop. Recorded radiographic evidence of cerebral edema, subdural hematoma, and intracranial hemorrhage on first head CT)
- implementation (reach, dose, fidelity from medical records),
- organizational (annual trauma volumes, and physician & nurse staffing)

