### **3.4 Screening and Eligibility Criteria**

All pediatric patients who admitted to the ICU at a study hospital site with a TBI are screened and their families/guardians are approached to enroll. Patients who are not eligible at admission but deteriorate are included at the time deterioration is assessed. No other exclusions.

To be included the patient must be:

- Age < 18 years
- Mechanism or CT evidence of TBI
- Glasgow Coma Scale (GCS) Score  $\leq 8$  (if intubated, motor GCS  $\leq 5$ )
- Admitted to ICU at any point in the hospital stay

An enrollment log will be kept in the secure database. Reasons for non-enrollment (does not meet eligibility criteria, death before consent, consent refusal, withdrawal) will be documented.

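### The SAP names no baseline adjustment set for its mortality and GOSE-Peds models, and its covariate list leaves out GCS, the severity measure that defines eligibility (minor; secondary outcomes only)

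*SAP*

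**What the plan says.** **Eligibility.** Protocol 3.4 requires a "Glasgow Coma Scale (GCS) Score" of 8 or less, with a motor criterion of 5 or less for intubated children ("if intubated, motor GCS"). GCS must therefore be assessed for every child before entry.

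**Covariates.** The SAP list begins "patient (demographics, ISS, LOS, presence of extracranial injuries", continues with surgery in the first 7 days, and adds "Recorded radiographic evidence of cerebral edema, subdural hematoma, and intracranial hemorrhage on first head CT". Implementation measures and organizational factors follow. GCS appears neither there nor elsewhere in the SAP. The injury characteristics to be compared under Methods item 1 are not itemised.

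**Models.** For in-hospital mortality and dichotomised 3-month GOSE-Peds, Methods item 3 plans "Poisson regression with robust variance estimation and clustering by site to estimate separately the relative likelihood of program implementation on these outcomes", with no covariates named. For later mortality it plans a "Multivariable Cox regression model to examine the marginal effect of PEGASUS on mortality during the 3 months post discharge", averaged over centers, again without listing covariates. The SAP asks whether any imbalances between arms need to be addressed, but gives no rule for addressing them.

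**Design.** Protocol 3.3 ranks the 16 sites on three measures of enrolment volume and randomizes within four groups, 8 sites per arm. Protocol 3.7 says the trial is not sufficiently powered for mortality, discharge or three-month outcomes.

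**The concern.** The SAP's hypothesis includes better discharge survival and better 3-month GOSE, so these are planned comparisons between arms. Initial severity is an obvious prognostic variable for them, and the design does nothing to balance it. If the adjustment set is left open, any later adjustment for GCS will be chosen after the data are seen, and a difference in mortality may be hard to separate from a difference in case mix.

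The list also mixes baseline items with items that arise after randomization. LOS, surgery during the stay, and implementation dose and fidelity can all be affected by the arm, and LOS is cut short by death. If the whole list were taken as the adjustment set, the models would condition on consequences of the intervention while omitting a measurement made at entry.

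**Working it through.** **1. The plan's own figure.** Protocol 3.7 gives 432 children, ICC 0.05, 58.6% adherence in controls, a difference of 18.7 (taken as percentage points, so 77.3%), two-sided 5% and 80% power.
- Children per site: 432/16 = 27. Design effect: 1 + 26 × 0.05 = 2.3. Effective number per arm: 216/2.3 = 93.9.
- SE = √[(0.586 × 0.414 + 0.773 × 0.227)/93.9] = 0.0667. Then 0.187/0.0667 − 1.96 = 0.84, so power is 80.0%.

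The figure reproduces. It concerns adherence and contains no GCS term, so this point leaves it unchanged.

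**2. Chance imbalance in GCS.** The documents give no GCS distribution. Assume scores 3 to 8 equally likely, so SD = 1.71. The SE of the difference between arms is 1.71 × √[2(1 + 26 × ICC)/216].

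| GCS ICC (assumed) | SE | 95% range | In SD units |
|---|---|---|---|
| 0 | 0.164 | ±0.32 points | 0.19 |
| 0.05 | 0.249 | ±0.49 points | 0.29 |
| 0.10 | 0.312 | ±0.61 points | 0.36 |

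**3. Precision.** Trials were simulated with 16 sites of 27, randomization within four groups, total GCS 3 to 8 and control mortality about 30%. Each was analysed by a log-link Poisson model with arm alone and with arm plus GCS, 2,000 trials per cell. Cells give the ratio of the SDs of the log risk ratio (adjusted/unadjusted) and the variance reduction, 1 − ratio².

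| Setting | OR per point 1.0 | 0.85 | 0.7 | 0.6 |
|---|---|---|---|---|
| GCS ICC 0, no site effect on outcome | 1.001; 0% | 0.994; 1% | 0.973; 5% | 0.942; 11% |
| GCS ICC 0.05, site SD 0.3 (logit) | 1.002; 0% | 0.996; 1% | 0.970; 6% | 0.917; 16% |
| GCS ICC 0.05, no site effect on outcome | 1.003; about 0% | 0.996; 1% | 0.947; 10% | 0.892; 20% |

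Repeating this with an event rate of 25% and odds ratios from 0.85 to 0.5 gave reductions of about 2-10% at ICC 0 and 3-18% at ICC 0.05. A separate set of 1,000 runs per cell at ICC 0.05 gave about 8%, 13% and 22% for odds ratios 0.7, 0.6 and 0.5. Taken together, the range is roughly 0-20%.

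**4. What the simulations leave out.** The comparison model has no other covariates, so the gain beyond ISS and first-CT findings was not estimated and is probably smaller. Total GCS was simulated; the motor score alone is coarser and would probably gain less.

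**The case against.** - **The omission may change nothing by itself.** A reader might infer that leaving GCS off the list removes it from the mortality and GOSE-Peds models. The SAP never says that the list enters the Poisson models, which may be unadjusted as written. This stands: the underlying gap is the unstated adjustment set, and adding GCS to the list alone would not fill it.
- **Severity is partly covered.** If the list is used, ISS, extracranial injury and CT findings are on it. This stands, and it limits the gain.
- **A large gain is not supported.** A variance reduction near 46% appeared only with a GCS ICC of 0.20 and an odds ratio of 0.5 per point, which means 2⁵ = 32-fold odds between GCS 3 and 8. At an odds ratio of 0.85 the reduction is about 0-4% for ICCs from 0 to 0.20.
- **The Cox model differs.** A reader might expect adjustment to shrink its standard error. It changes the hazard ratio being estimated and does not generally do so. The case there is protection against imbalance and possibly power.
- **Bias is not shown.** Arms are known at enrolment, so a reader might infer that severity differs systematically by arm. Protocol 3.4 screens all pediatric TBI admissions to the ICU and logs reasons for non-enrolment, and nothing in the documents shows selection by arm. Chance imbalance is an issue of precision and interpretation, not systematic bias.
- **GCS is not perfectly clean or certain to be stored.** Children who deteriorate are enrolled at that time, so their eligibility score may follow ICU care at an openly assigned site. The protocol text mentions the motor score only for intubated children and does not say that it is recorded for all. Both caveats stand and belong in the fix.

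None of this removes the case for prespecifying a severity measure that has to be assessed for every child.

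**Conclusion.** The point holds as a minor one. The SAP gives no adjustment set for two Poisson models and one Cox model of patient outcomes, and its covariate list omits the severity measure used for entry. Volume-only stratification of 16 sites leaves room for a chance difference in mean GCS of about 0.2 to 0.36 SD, given an assumed SD of 1.71 and GCS ICCs of 0 to 0.10. The likely fall in the variance of the log risk ratio is roughly 0-20%. That rests on assumed event rates of about 25-30%, an assumed GCS-outcome association and models with no other covariates; the documents supply none of these. Only secondary outcomes that the protocol already calls underpowered are affected.

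**What to change.** In SAP Methods item 3, before outcomes are compared by arm:

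1. Name the baseline covariates for each of the three models: eligibility GCS (motor score for all, so that intubated children are included), demographics, ISS, extracranial injury and first-CT findings. State an order of priority in case there are too few events for all of them. As a guide, 25% of 432 would be 108 in-hospital deaths; the number in the Cox period cannot be derived from the documents.
2. State that LOS, surgery and implementation dose or fidelity are not baseline adjusters, because they arise after randomization.
3. For the Cox model, say that the marginal effect is obtained by averaging over the covariates as well as over centers.
4. Confirm that the motor score and its time are stored for every child, including those enrolled on deterioration, and say how a missing score is handled.

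The cost is a few lines in the SAP and one check of the database. The sample size and the primary analysis do not change. If the motor score proves not to be stored for every child, it would have to be abstracted from the records.

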### **1.1 Specific Aims**

- 1) Determine the relationship between PEGASUS program implementation and TBI guideline adherence (Aim 1a) and assess system, provider, patients, implementation, and guideline factors associated with TBI guideline adherence (Aim 1b).
- 2) Create a value stream map (VSM) that readily identify value added process of care associated with TBI guideline adherence.
- 3) Use computer simulation to develop and disseminate a real-world best practices blueprint for TBI guideline adherence.

This is a necessary advance and a step towards implementing guideline-based TBI care for children who suffer from TBI.

\*\*A cost analysis component is also included, although it is not a separate aim.

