### **3.8 Recruitment, Retention & Follow-up**

Recruitment is limited to eligible patients admitted and consented at study sites. Based on baseline recruitment levels, the target sample size of 432 is feasible with about 9 participants per site per year. This is an in-patient intervention for the first 7 days of ICU care where intervention ICU staff are trained on intervention delivery as part of their patient care. Other data will be obtained from the health records. Follow-up data collection will be attempted at three months post-admission and can be completed in-person, via telephone, or from the health record. If unable to complete follow-up by four months, the participant will be designated lost-to-follow-up, but in-hospital data will be included. There is no incentive for participation offered to patients at any stage.

[figure not shown]

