## 4.4 PEGASUS Pathway

[figure not shown]
The PEGASUS pathway does not prescribe specific drug doses or treatments but provides guidelines that inform the clinical assessment and treatment for individual patients. The PEGASUS program has been iteratively refined for use in the South American context and includes additional nursing resources for rounding and family education guides to encourage engagement.

As a pragmatic implementation science study with quality improvement efforts, the components of the study are designed to be adaptable to support sites' needs and to evaluate process measures to address reach (number of patients), dose (% processes implemented), and fidelity (variance from recommended

processes and timely clinical pathway adoption). The Theoretical Domain Framework (TDF) and the Determinants of Implementation Behavior Questionnaire (DIBQ) guide these efforts.

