## **5.2 DSMB Committee**

This study has an internal Data Safety and Monitoring Board (DSMB) comprised of a small group of experts who are not part of the study team. Study PIs, CIIC co-investigators, and the research coordinator will meet with them twice per year to review study status, recruitment, and adverse events, or in the event of an escalation.

The DSMB will review participant recruitment, mortality, surgery type and frequency, and adverse events from the complications form. The study team will categorize complications according to body system. The DSMB will remain blinded to study arms unless a specific, unanticipated concern needs to be addressed. Reports from the meetings will also be submitted to the UW IRB to comply with IRB requirements.

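### The SAP lists delivery measures (reach, dose, fidelity) and post-assignment variables (LOS, surgery to day 7) as covariates or confounders, which exposes the per-protocol and Cox arm effects

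*SAP*

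**What the plan says.** The SAP, which covers Aim 1a only, has a single Covariates/confounders list and does not assign it to any model. Besides organisational variables and first-CT findings, it contains "patient (demographics, ISS, LOS, presence of extracranial injuries, and surgery (yes/no) for up to 7 days after severe TBI" and "implementation (reach, dose, fidelity from medical records".

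Other places bear on those items:

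- Protocol 4.4 treats them as process measures of the programme: "reach (number of patients), dose (% processes implemented), and fidelity (variance from recommended" processes, with timely adoption of the pathway.
- Protocol 1.1 gives implementation factors a separate place: "assess system, provider, patients, implementation, and guideline factors associated with TBI guideline adherence (Aim 1b".
- Protocol 3.8 sets the treatment window: "This is an in-patient intervention for the first 7 days of ICU care". Surgery is recorded over up to 7 days after injury.
- SAP Methods item 2 gives the ITT model without covariates. The per-protocol model is the same, but "potentially including implementation dose/fidelity as covariate and interaction with intervention".
- SAP Methods item 3 gives two Poisson models without covariates, and a Cox model that is called multivariable but names none.
- SAP Questions of interest, item 2, asks whether arm imbalances have to be dealt with, and so leaves adjustment open.

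**The concern.** A confounder of a randomised comparison must precede assignment or be independent of it. Reach, dose and fidelity follow from arm. Conditioning on them removes whatever part of the effect runs through delivery, which is how the programme is meant to work. Surgery within the treatment window and LOS, known only at discharge or death, are also later than assignment. If the programme alters either, adjusting for it removes or distorts part of the effect.

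At stake is how two non-primary results are read. A dose-adjusted arm coefficient near zero with a wide interval could be reported as a weak programme effect when it answers a different question. The Cox model aims at a marginal effect of the programme on mortality, yet the only covariate list its analyst could draw on includes possible consequences of the programme.

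**Working it through.** **1. The plan's own figure.** From Protocol 3.7: control adherence 58.6%, difference 18.7 points (77.3%), ICC 0.05, N = 432. There are 16 sites, so 432/16 = 27 per site and 216 per arm.

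- Design effect = 1 + 26 × 0.05 = 2.3.
- SE = √[(0.586×0.414 + 0.773×0.227) × 2.3/216] = 0.0667.
- 0.187/0.0667 = 2.80. Power is 80.0% by the normal approximation, which reproduces the protocol, and 74.1% by noncentral t with 14 df. The 74% is the reference below.

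**2. Can the full per-protocol model be estimated?** The documents do not state a control-site dose. If it is 0 (assumption), the dose and arm × dose columns are identical. The design matrix has rank 3 of 4, so both terms cannot be estimated.

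**3. Arm plus uncentred dose, control dose 0, one dose value per site.** The arm coefficient is then the effect at zero dose. SE ratio = √[1 + 4·mean²/(7·SD²)], with power on 13 df. Means and SDs over the 8 intervention sites are assumptions.

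| Mean | SD | SE ratio | Power for 18.7 points |
|---|---|---|---|
| 0.5 | 0.10 | 3.91 | 10% |
| 0.5 | 0.15 | 2.71 | 16% |
| 0.5 | 0.25 | 1.81 | 30% |
| 0.7 | 0.10 | 5.39 | 8% |
| 0.7 | 0.15 | 3.67 | 11% |
| 0.7 | 0.25 | 2.34 | 20% |

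**4. The same, with dose also varying between patients within a site.** The SAP's Potential products include a figure of such variation. Let v = 0.773×0.227 = 0.1755. Information on the dose slope is I = 7·SDb²/(v×2.3/27) + 8×26·SDw²/(v×0.95), where SDb and SDw are the between-site and within-site SDs. Then Var(arm) = 0.0667² + mean²/I.

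- Mean 0.5, SDb 0.25, SDw 0.25: I = 107.2, ratio 1.23, power 56%.
- Mean 0.7, SDb 0.10, SDw 0.10: I = 17.2, ratio 2.72, power 16%.

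Step 3 uses a residual variance common to both arms. Using the arms' average, (0.2426 + 0.1755)/2 = 0.209, for v here gives 1.3-2.9 and 14-53%, so the picture is the same.

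**5. Control dose measured and non-zero (site level, assumed).** Ratio = √[1 + 4·(difference in means)²/(7·(SDc² + SDi²))].

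- Control 0.1 (SD 0.10), intervention 0.7 (0.10): 3.36, power 12%.
- Control 0.2 (0.15), intervention 0.7 (0.15): 2.04, power 25%.
- Control 0.3 (0.15), intervention 0.5 (0.25): 1.13, power 63%.

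The model can be fitted here, but it still adjusts for a consequence of assignment.

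**6. Shrinkage.** Steps 3-5 assume that none of the effect runs through dose. If 0, 50 or 100% does, the expected arm coefficient with control dose 0 is 18.7, 9.4 or 0 points. In simulated Poisson fits the RR is about 1.32, 1.17 and 1.03. It is not exactly 1 at full mediation because the simulated effect is additive and the model is log-linear. Without dose in the model the RR stays at 0.773/0.586 = 1.32.

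**7. Coding.** With dose centred within the intervention arm, the arm estimate is unchanged; simulated rejection was 71-73%, against 72-75% without dose.

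**8. Cox model.** The documents give no death rate and no effect on surgery or LOS, so no size follows. LOS is partly the outcome only if in-hospital deaths count. Methods item 3 refers to the period after discharge, while the planned figure is labelled 3-month mortality.

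**The case against.** The case against a broad reading is good, and much of it stands.

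- A reader might infer that the primary result is biased. The documents do not support that: the ITT model names no covariates, and the per-protocol wording implies that ITT omits dose/fidelity. A reader might equally infer that the ITT and secondary Poisson models are certainly unaffected. That is also too strong. For LOS and surgery it rests on silence, because the list heads the whole Aim 1a plan and adjustment for imbalance is left open.
- The 1.8-5.4 ratio might be taken as the expected loss. It assumes one dose value per site, whereas the SAP expects variation within sites; hence the lower range in step 4.
- The per-protocol loss depends on uncentred coding in an analysis that is only potential, and the SAP never says that this coefficient will be reported as the programme effect. This stands, but the coding is unstated, and centring does not rescue the interaction if control dose is constant.
- DSMB review ("The DSMB will review participant recruitment, mortality, surgery type and frequency, and adverse events from the complications form") might be read as evidence that assignment affects surgery. It is routine monitoring and shows no such thing.
- The list may be partly a data inventory. The heading and the per-protocol line weaken that reading but do not exclude it.
- The bivariate comparisons in Methods item 1 ("Potential differences in patient (age, sex, race/ethnicity) and injury characteristics will be examined using bivariate analyses by center") name only patient and injury characteristics and are not at fault.

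**Conclusion.** The point holds in limited form. Five listed variables are delivery measures or arise after assignment and should not adjust the arm effect. The per-protocol and Cox models are exposed; the ITT and secondary Poisson models are unaffected only if fitted without these variables, which the SAP does not say.

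For the per-protocol model with control dose 0 and uncentred dose, the SE of the arm coefficient is about 1.8-5.4 times larger (site-level dose) or 1.2-2.7 times (dose varying within sites). Power for 18.7 points is about 8-56% instead of 74%, before any shrinkage through mediation. The control dose, dose means and SDs, and mediation shares are all assumptions. The failure to estimate the interaction needs only a constant control dose. No size can be given for the Cox model, an effect of the programme on LOS or surgery is not shown, and no bias in the primary result is shown.

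**What to change.** 1. State that reach, dose, fidelity, LOS and surgery adjust the arm effect in no model, including ITT and secondary Poisson. Report them descriptively by arm where collected.
2. For the Cox and any other adjusted model, name a short set that the intervention cannot affect, for example age, ISS, extracranial injury and first-CT findings. Keep it small relative to the number of deaths, and state whether in-hospital deaths count.
3. Replace the per-protocol covariate/interaction model with an exploratory, non-randomised dose-response within the 8 intervention sites, linked to Aim 1b. With control dose 0 it estimates essentially the same slope, but leaves no arm coefficient to misread. It will be imprecise: at site level the 95% half-width per 0.1 of dose is 0.1 × t(6 df) × √[0.1755×2.3/27/(7·SD²)], about 11 points at SD 0.10 and 4.5 at SD 0.25.
4. As a separate improvement, include the randomisation enrolment group (Protocol 3.3; three terms) and, where available, site baseline adherence from the September 2019-September 2020 data (Protocol 8.4) in the primary model. This uses 4 of 14 df. With 10 df and SE × √(1 − R²), power is 71% if the terms explain none of the site-mean variance, 81% if 20% and 94% if 50%, against 74% now. Break-even is about 6%. The R² values are assumptions.

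Items 1-3 need only a SAP amendment and no new data. Item 4 changes the primary model, so it must be fixed before outcome data by arm are seen.
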